8.11.8 Reporting of Adverse Events of Special Interest (AESIs)

CCI

In case of difficulty to obtain all the required information within 24 hours, an initial report can be submitted with follow up information provided within 24 hours of awareness of the new information.

The following information should be provided when reporting an AESI:

- Subject identification (subject number and initials)
- Event description including observed symptoms
- Medical history related to event
- Event onset date and time
- Depth of injections
- Interventions implemented to treat event
- Event outcome (with resolution date and time if applicable)
- Relatedness to study product or procedure
- Seriousness of event
- Study treatment information (number of injections, date of injections, name of product injected, volume injected, injection tool used etc.)

If the Investigator assesses an AESI to be serious, an SAE report should be submitted as specified in section 8.11.7.

Upon receipt of the AESI report, the Sponsor/CRO Medical Expert(s) will further evaluate and document the evaluation of the reported incident.

If any of the following events occur the Sponsor will expedite the report to FDA, within 10 days and to the IRB as applicable:

1. All incidences of visual disturbances (loss of vision, blurry vision, double vision, pain in or around the eye, blind spot or shadow in the visual field, trouble moving the eyes), regardless of relationship to study product or seriousness;
2. Any worsening in visual acuity (i.e. negative change of one line or greater) related to the treatment procedure or study product;
3. Any abnormal results on extraocular muscle function test or confrontation visual field;
4. A medical concern that requires continued monitoring of the patient's condition in regard to an AESI or if additional examinations may be needed, as assessed by the Investigator (e.g. referral to an eye specialist).

8.11.9 Reporting of unanticipated adverse device effect

□

An Investigator shall prepare and submit a complete and accurate report to the Sponsor/CRO, for contact details see section 8.11.7, and to the reviewing IRB on a suspected UADE as soon as possible, but in no event later than 10 working days after the Investigator first learns of the effect, in accordance with FDA regulation CFR 812.150.

8.11.10 Stopping rule

Enrollment and treatment in the study will be temporarily halted if a serious adverse event (SAE) occurs for the following:

any unanticipated SAE which is possibly related to the study device or procedure including but not limited to a vascular embolic event that leads to skin necrosis, vision loss or stroke, damage to facial nerves which may result in facial paralysis or injury to internal facial structures.

The SAE will be investigated by the Sponsor. If the Sponsor's investigation concludes the SAE:

- was unanticipated,
- directly related to the study product or device injection procedure,
- and presents an unreasonable risk to study subjects, the study will be terminated, and the Investigators will be notified. The IRB and RA will also be notified if the study is prematurely terminated due to safety concerns. If the SAE does not meet the above criteria, then enrollment in the study will continue.

8.11.11 Follow-up of unresolved events ongoing at termination of the study

All serious as well as non-serious AEs with a causal relationship to the study product or treatment procedure and ongoing at study end, shall be followed up after the subject's participation in the study is over. Such events shall be followed-up after the last study visit until resolved, assessed as chronic or stable, or subject is lost to follow up. Final outcome after the end of the study shall be reported on the AE Follow-up form.

8.11.12 Reporting and follow-up of events occurring after subject termination of the study

All Adverse Events with a causal relationship to the study products or treatment procedure that the Investigator becomes aware of, serious as well as non-serious, with onset after the study termination (subject's last study visit) shall be reported to the Sponsor by email to [contact]. The Investigator shall follow the subject until the event is resolved.

8.11.13 Pregnancy

Pregnancy itself is not regarded as an AE. If there is a pregnancy during the study period, the subject must be withdrawn from any following study treatment but should continue to be followed within the study and the outcome of pregnancy must be reported even if the delivery occurs after study completion.

A pregnancy confirmed during the study period must be reported by the Investigator on a pregnancy report form immediately upon acknowledge and be submitted to the Sponsor

	
CCI
 

 

 
Title CTN 43BBJ1911 US Jawline, Clinical Investigation Plan

---	--

according to contact details specified in section 8.11.7. The report can be prospective or retrospective. Follow-up shall be conducted to obtain outcome information on all prospective reports.

Cases that led to fetal distress, fetal death or a congenital abnormality or birth defect are to be regarded as SAEs and shall be reported on the exposure *in utero* report form to the Sponsor immediately but no later than 24 hours after the Investigator's awareness. These events shall be handled as SAEs during data processing. Other complications during the pregnancy that are related to the pregnant woman and fulfils any serious criteria, such as pre-eclampsia requiring hospitalization, shall be reported, and handled as SAEs. Elective abortions without complications shall not be reported as AEs.

8.11.14 Anticipated Adverse Events

Information regarding anticipated AEs for GP0109 is included in the study specific IFU.

8.12 **Device deficiencies**

8.12.1 Definition of a device deficiency

A device deficiency is defined as an inadequacy of a medical device with respect to its identity, quality, durability, reliability, safety⁴, or performance.

Note: Device deficiencies include malfunctions, use errors, and inadequate information supplied by the manufacturer.

[figure not shown]
8.12.2 Recording instructions

When a device deficiency is discovered, Part A of the clinical study complaint form shall be completed by the Investigator. The type of complaint shall be described and injury to the subject or user or unintended exposure to study product shall be reported as applicable. If an injury has occurred, an AE or an SAE form shall be completed as applicable (refer to sections 8.11.6 and 8.11.7). If no SAE was experienced as a result of the device deficiency the Investigator shall assess whether or not the device deficiency *could have led* to an SAE if:

- Suitable action had not been taken, ☐ Intervention had not been made, or
- Circumstances had been less fortunate

In Part B of the clinical study complaint form, the Sponsor will make the same assessment.

8.12.3 Reporting of device deficiencies

⁴ Inadequacy of device safety refers to properties of the device which could have or have led to an AE.

GALDERMA <small>EST. 1987</small>	Title CTN 43BBJ1911 US Jawline, Clinical Investigation Plan
---	--

□

A device deficiency that led to an SAE and any device deficiency that could have led to an SAE shall be reported to the Sponsor within 24 hours after the Investigator's awareness (for contact information, see section 8.11.7).

If the Investigator or the Sponsor assesses that the device deficiency could have led to an SAE the Sponsor is responsible for reporting the device deficiency to RA and the PI is responsible for reporting it to the IRB.

The deficient study product shall be kept by the study site until the Sponsor has confirmed whether the product shall be returned to Sponsor for further study or if it can be destroyed at the study site.

9. Data Handling and Management

9.1 Data management

Data management based on GCP refers to the activities defined to achieve safe routines to enter clinical data information into a database, efficiently and avoiding errors. The data management routine includes procedures for database set-up and management, data entry and verification, data validation, and documentation of the performed activities including information of discrepancies in the process. The data management process will be described in detail in the data management plan (DMP).

The database, the data entry screens, and program will be designed in accordance with the CIP and the eCRF template. Data validation will be performed by computerized logical checks and manual review. Drugs and events will be coded in accordance with World Health Organization (WHO) Drug and Medical Dictionary for Regulatory Activities (MedDRA) dictionaries as specified in the DMP. Safety data (SAE and if applicable AE of special interest) in the clinical database will be reconciled against the data in the safety database.

When all efforts have been made to ensure that the data recorded in the eCRFs and entered in the database is as correct and complete as possible, the clinical database will be locked. Study data will be transferred to SAS datasets, which thereafter will be write-protected. Statistical analyses will be generated in SAS using data from the locked datasets.

9.2 Electronic Case Report Forms

A 21 Code of Federal Regulations Part 11-compliant electronic data capture application will be used to collect, modify, maintain, archive, retrieve, and transmit study data. An electronic Case Report Form (eCRF) is required and should be completed electronically for each screen failure as well as enrolled subjects.

The eCRF includes password protection and internal quality checks, such as automatic range checks, to identify data that appear inconsistent, incomplete, or inaccurate. Study data should be entered directly from the source documents, which are to be defined at each site before inclusion of the first subject.

Authorized study site personnel designated by the Investigator should complete data collection. Appropriate training and security measures should be completed with all authorized investigation site personnel prior to the study being initiated and any data being entered into the system for any subject.

The study data is the sole property of the Sponsor and should not be made available in any form to third parties, except for authorized representatives of appropriate RA, without written permission from the Sponsor. At the end of the study, electronic data are kept at the Sponsor and a copy (provided by the vendor) at the study site as part of the Investigator file.

Any delegation of collection of data should be specified in a signature and delegation log.

9.2.1 Data entry

All data shall be entered in English. The eCRFs should always reflect the latest observations on the subjects participating in the study. Therefore, the eCRFs shall be completed as soon as possible during or after the subject's visit. The subject's identity must always remain confidential, i.e. the name and address of the subjects must not be registered in the eCRFs or

	

Title	

CTN 43BBJ1911 US Jawline, Clinical Investigation Plan	

	Title	CTN 43BBJ1911 US Jawline, Clinical Investigation Plan	
Title				
CTN 43BBJ1911 US Jawline, Clinical Investigation Plan				

in the database. The Investigator must verify that all data entries in the eCRFs are accurate and correct. If some assessments are not done, or if certain information is not available, not applicable or unknown, the Investigator shall indicate this in the eCRF. The Investigator shall electronically sign off the study data. By signing, the Investigator takes responsibility for the accuracy, completeness, and legibility of the data reported to the Sponsor in the eCRF.

9.2.2 The query process

The monitor shall review the eCRFs and evaluate them for completeness and consistency. Each eCRF shall be compared with the respective source documents to ensure that there are no discrepancies between critical data. All entries, corrections, and alterations shall be made by the PI or his/her authorized designee. The monitor cannot enter data in the eCRFs. Once study data have been submitted to the central server via the eCRF, corrections to the data fields will be audit trailed, meaning that the reason for change, the name of the person who made the change, together with time and date will be logged. Roles and rights of the site personnel responsible for entering study data into the eCRF shall be determined in advance. If discrepant data is detected during review of the data, either by the Sponsor or by its representatives, the responsible data manager or monitor shall raise a query in the electronic data capture application. The query shall state the question or data to be changed and shall be resolved in the system by the PI or his/her authorized designee. The appropriate study site personnel shall answer the queries in the eCRF. This will be audit trailed by the electronic data capture application meaning that the name of study site personnel, time, and date is logged.

9.2.3 User identification

The eCRF records will be automatically appended with the identification of the creator, by means of their unique UserID. Specified records shall be electronically signed by the Investigator to document his/her review of the data and acknowledgement that the data are accurate. This will be facilitated by means of the Investigator's unique UserID and password; date and time stamps will be added automatically at time of electronic signature. If an entry in an eCRF requires change, the correction shall be made in accordance with the relevant software procedures.

9.2.4 Audit trail

All changes will be fully recorded in a protected audit trail and a reason for the change shall be stated. Once all data have been entered, verified, and validated, the database will be locked.

9.3 **Source documents**

Source documents are all documents used by the Investigator or hospital that relate to the subject's medical history, that verifies the existence of the subject, the inclusion and exclusion criteria, and all records covering the subject's participation in the study. They include laboratory notes, memoranda, material dispensing records, subject files, etc.

The Investigator is responsible for maintaining source documents. These should be made available for inspection by the monitor at each monitoring visit. The Investigator must submit a completed eCRF for each subject for whom signed informed consent has been collected. All supportive documentation submitted with the eCRF, such as laboratory or hospital records, should be clearly identified with the CTN and subject number. Any personal information, including name, should be removed or rendered illegible to preserve individual confidentiality.

9.4 Record keeping and access to source data

The Investigator/Institution should permit study-related monitoring, audits, IRB review, and RA inspections and should provide direct access to the source data/medical record including the identity of all participating subjects (sufficient information to link records, i.e. eCRF, medical records, original signed ICFs and detailed records of study product accountability). The records should be retained by the Investigator as required by local legislation and international guidelines. Any transfer of responsibility for storage of the records should be documented and the Sponsor should be informed in writing.

The Sponsor should verify that each subject has consented in writing to direct access to the original medical record/source data (by the use of written subject information and signed informed consent). The data recorded in the eCRFs will be checked for consistency with the source documents/medical record by the monitor during monitoring (source data verification; SDV). In order to be able to perform SDV, information about each subject's participation in the study has to be detailed in the medical record.

9.5 Document and data retention

All records pertaining to the conduct of the study, including signed eCRFs, ICFs study product accountability records, source documents, and other study documentation must be retained for as long as is specified in the CTA. Measures should be taken to prevent accidental or premature destruction of these documents (e.g. protection against damage and unauthorized access, preferably by storage in a fire-proof cabinet).

It is the Investigator's responsibility to inform the Sponsor in writing if the Investigator file is moved or if the responsibility for the documents is transferred to someone else.

9.6 Clinical Study Report

Two Clinical Study Reports (CSRs) will be compiled; an interim CSR, see section 10.8 and a CSR after completion of the whole study. A summary of the study results will be published on a public database, <http://www.ClinicalTrials.gov>.

10. Statistical Methods

10.1 General

A comprehensive Statistical Analysis Plan (SAP) with detailed description of all statistical analyses will be developed before database lock.

All study data will be listed in subject data listings.

All statistical analyses, including summary tables and data listings, will be performed using SAS. Confidence intervals (CIs) will be two-tailed and constructed at a confidence level of 95%. Statistical tests will be performed at a significance level of 5%, and p-values will be twosided, unless otherwise specified.

Continuous endpoints will be summarized using descriptive statistics, e.g. number of subjects (n), mean, median, standard deviation, minimum and maximum values. Categorical endpoints will be presented in frequency tables with number and percentage of observations for each level.

	Title CTN 43BBJ1911 US Jawline, Clinical Investigation Plan	
---	---	--

10.2 Analysis populations

The following populations will be defined:

- Intention-to-treat (ITT) Includes all subjects who are randomized and will be analyzed according to the randomization scheme
- Per protocol (PP) Includes all subjects in ITT who complete the 3 months after baseline visit, without any deviations considered to have substantial impact on the primary effectiveness outcome
- Safety Includes all subjects who were treated with GP0109 or randomized to the control group, and will be analyzed according to as-treated principle

Intention-to-treat is the primary population for all efficacy analyses. If the PP population contains less than 90% of the subjects in the ITT, a sensitivity analysis of the primary efficacy endpoint will be performed based on the PP population. Safety analysis is performed based on the safety population set.

The disposition of subjects will be presented in tables and/or figures as appropriate. The number of screened, randomized, treated, completed, and withdrawn subjects will be presented, as well as number of subjects in each analysis population set.

10.3 Demographics, baseline assessments, and subject characteristics

Demographic endpoints, baseline assessments, and subject characteristics will be presented based on the ITT analysis set using descriptive statistics by treatment, as appropriate.

10.4 Effectiveness analysis

10.4.1 Primary effectiveness analysis

Responder rate based on the GJS, as assessed live by the Blinded Evaluator at Month 3 after baseline, will be the primary effectiveness endpoint. A responder will be defined as a subject with at least 1 grade improvement from baseline on both sides of the face concurrently.

The null hypothesis will be that there is no relationship between responder rate and treatment group (i.e. the responder rate is the same in treated and untreated subjects). The alternative hypothesis will be that there is a relationship between responder rate and treatment group (i.e. the responder rate is different in treated subjects compared to untreated subjects).

The estimates of the responder rate in each treatment group will be presented as well as the difference in responder rates. Corresponding confidence intervals for responder rates and the difference in responder rates along with the p-value for the difference will also be presented.

First, the Breslow-Day test for homogeneity of odds ratios will be used to assess consistency of GJS odds ratios across all strata (the needle-treated group, the cannula-treated group, and the combination group). A significance level of 0.05 will be used to determine if the responder rates are non-homogenous. If the Breslow-Day p-value is less than or equal to 0.05, the primary analysis will be stratified (i.e. conducted separately) for the needle treated group, the cannula-treated group, and the combination group, using a significance level of 1.7% to account for multiplicity. If the Breslow-Day p-value is greater than 0.05, the analysis will be carried out on

GALDERMA <small>EST. 1987</small>	Title CTN 43BBJ1911 US Jawline, Clinical Investigation Plan
---	--

pooled groups, using a significance level of 5%. Regardless of whether the primary analysis will be based on pooled injection tool groups, or done separately, the no treatment control subjects will be pooled across all study sites. Fisher’s exact test will be used to compare the responder rates between the treated and untreated subjects at Month 3.

In order to assess the poolability of study sites, a Breslow-Day test for homogeneity of odds ratios across sites will be performed. If the p-value of the sites test is <0.05, then subgroup analysis by study sites will be done.

CCI

CCI

	
Title
 
CTN 43BBJ1911 US Jawline, Clinical Investigation Plan
	
---	--	--

10.5 Safety analysis

All AEs will be coded according to MedDRA and summarized by system organ class (SOC), preferred term (PT) and treatment (no treatment, 1st treatment including touch-up if applicable, and 2nd treatment).

A summary of all AEs will be provided, which will include:

- number of subjects with at least one AE and number of events (in total as well as serious AEs)
- number of subjects with at least one related AE and number of events (in total as well as serious AEs)
- number of subjects with at least one unrelated AE and number of events (in total as well as serious AEs)
- number of subjects who did not have an AE

The number of subjects with AEs related to study product or injection procedure as well as the number of events will be summarized by SOC, PT and maximum severity. In addition, for related AEs the number of days to onset and the duration of event will be summarized by SOC and PT using mean, SD, min, max and median. Action taken for related AEs will also be summarized. Serious AEs, and AEs with onset >21 days after most recent treatment will be listed.

Non-related AEs will be summarized by SOC, PT and intensity.

To evaluate consistency of AEs across different subgroups, AEs will also be summarized by subgroups defined as described below.

Safety analysis will be descriptive only.

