Treatment regimen and location of treated area:	
In the study, the treatment area extends from the mandibular angle, through the jawline and including the post- and pre-jowl area (from tip of ear to tip of chin) in order to create a smooth correction that blends well with the adjacent structures.
 
Subjects in the treatment group will receive one GP0109 treatment at baseline and one optional touch-up treatment at 1 month.
 
Subjects in the no treatment group will be offered an optional GP0109 treatment at 12 months. The subjects who received treatment at baseline will also be offered an optional re-treatment at the month 12 visit, if aesthetic improvement is not maintained (as determined by the Treating Investigator and subject).
 
Sites will be selected to use either needle, cannula or a combination for injection of all subjects at their site. The injection technique is at the Treating Investigator's discretion in the deep subcutaneous tissue or supraperiosteal plane. Depending on the location and injection tool, serial puncture (needles), tunneling, and linear threading among other techniques can be used to safely and effectively enhance the contour, shape and definition of this aesthetic region. The injection technique and the use of needle/cannula per treated area will be recorded.
 
Aspiration is recommended prior to each injection.
 
It is recommended to start injection with small aliquots at the edge of the angle of the mandible in the deep subcutaneous tissue or supraperiosteal to enhance the mandibular angle. Once the mandibular angle is defined, continue the correction with the mandible body with a threading technique medially and inferior to the masseter and the post-jowl sulcus using needle or cannula. The antegonial notch injection where facial artery is should be avoided; in this area, subcutaneous injection is recommended. The ascending mandibular ramus is recommended to be treated in the subcutaneous plane to avoid the parotid gland.
 
Injection into the masseter muscle should be avoided and attempts should be made to inject superficial to or deep below the masseter muscle. Care must be taken to avoid facial artery and vein, mental nerve and artery, parotid gland, superficial temporal artery and vein, marginal mandibular nerve.
 
Slow injection is recommended, and overcorrection should be avoided.
 
After each injection, the treated tissue may be massaged for a smooth placement of the filler and optimal jawline contouring.
 
Allowed maximum injection volume is 4 mL per treatment session and side of face, with a total maximum volume of 8 mL per treatment session. The injection can bridge all the way from the mandibular angle, post-jowl and to the pre-jowl area (from tip of ear to tip of chin). Treatment of chin area is allowed for achieving a smooth contour, however treatment of chin retrusion is not within the scope of the study.

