2.5.1 Treatment Administration, Post-injection Procedures, and Procedural Anesthetics

Treatment administration endpoints will be summarized for each treatment session (initial, optional touch-up, and optional re-treatment) by treatment area, including injection method, depth of injection, needle size, cannula size, and introducer needle for cannula.

The number of subjects with any post-injection procedures and procedural anesthetics will be summarized by type.

Injection volume will be summarized for each treatment session (initial, optional touch-up, initial + touch-up, optional re-treatment) and overall by treatment area.

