2.5.2 Adverse Events (AEs)

All AEs will be summarized relative to treatment session timing using the following categories:

- No Treatment at Baseline: For subjects who receive no treatment at baseline, include AEs before any optional GP0109 treatment at Month 12.
- Initial Treatment with GP0109: Pool AEs for the following (whether optional touch-up treatment received or not):
 - For subjects treated with GP0109 at baseline:
 - include AEs before optional GP0109 re-treatment at Month 12,
 - include AEs through end of study if no re-treatment at Month 12.
 - For subjects who receive no treatment at baseline, include AEs after initial GP0109 treatment at Month 12.
- Re-treatment with GP0109: For subjects treated with GP0109 at baseline, include AEs after optional GP0109 re-treatment at Month 12.

All AEs will be coded according to MedDRA and summarized by System Organ Class (SOC), Preferred Term (PT), and treatment session timing as described above. The number of subjects with at least one event, associated percentage, and number of events will be provided.

For subject counts, a subject will only be counted once per SOC and once per PT in cases where multiple events are reported for a subject within SOC or PT. For event counts, subjects with multiple events in a category will be counted for each event.

The number of subjects with AEs related to study product or study product injection procedure and unrelated AEs, as well as the number of events, will be presented by SOC, PT, and maximum intensity. Action taken for related AEs will also be summarized by SOC and PT using number of events. AEs related to study product or injection procedure with late onset (> 21 days after most recent treatment session) will be listed.

Serious AEs and AEs of special interest (AESIs) will be listed. See Section 8.2.1 of the protocol for a list of visual disturbances considered to be AESIs.

For AEs related to study product or study product injection procedure, the number of days to onset and the duration of event will be summarized by SOC and PT using mean, standard deviation, median, minimum, and maximum. Days to onset of an AE will be derived as the start date minus the date of most recent treatment session. Duration of an AE will be derived as the stop date minus the start date + 1. Missing stop date will not be imputed, and therefore no duration will be calculated in these cases.

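### The AE percentages for initial treatment and for re-treatment cover different numbers of injection sessions and different follow-up, so they are not like for like

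*Protocol*

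**What the plan says.** Protocol 10.5 sets the AE groups as "treatment (no treatment, 1st treatment including touch-up if applicable, and 2nd treatment". SAP 2.5.2 is more explicit, and SAP 2.1 says that the SAP prevails where the two differ.

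- **Initial category, touch-up:** "Initial Treatment with GP0109: Pool AEs for the following (whether optional touch-up treatment received or not".
- **Initial category, late-treated controls:** "For subjects who receive no treatment at baseline, include AEs after initial GP0109 treatment at Month 12".
- **Initial category, window:** AEs are counted up to re-treatment at Month 12, but otherwise the rule is "include AEs through end of study if no re-treatment at Month 12".
- **Re-treatment category:** "Re-treatment with GP0109: For subjects treated with GP0109 at baseline, include AEs after optional GP0109 re-treatment at Month 12".

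For each category the SAP gives the number and percentage of subjects with at least one event, and the number of events. The regimen in the protocol synopsis is: "Subjects in the treatment group will receive one GP0109 treatment at baseline and one optional touch-up treatment at 1 month". Exposure, unlike AEs, is reported by session in SAP 2.5.1: "Injection volume will be summarized for each treatment session (initial, optional touch-up, initial + touch-up, optional re-treatment". Safety is descriptive throughout (protocol 10.5, SAP 2.5).

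**The concern.** The chance that a subject has at least one event rises with the number of exposures and with the time observed. Protocol 4.4.2 expects treatment-related AEs within a few days of an injection, so a touch-up is a second exposure to the same kind of risk. One category can hold two such exposures per subject and up to 24 months of observation. The other holds one exposure and about 12 months.

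Anyone who reads the two percentages together may then credit re-treatment with a better profile that comes partly from the counting rule. The visible AE plan also gives no AE rate for the touch-up, although it is part of the regimen under study. SAP 2.6 intends the 12-month data for early regulatory submission, so these descriptive percentages are the safety evidence that will be read.

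**Working it through.** **1. The plan's own figure.** Protocol 10.11.5 gives about 80% probability of seeing at least one AE of 1% incidence in 168 treated subjects. 1 − 0.99^168 = 81.5%, so it reproduces. It treats each subject as one unit of exposure and does not address sessions.

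**2. Sessions per category.** The schedules of events place product injections only at Visits 1b, 3 and 7. Visits 7a to 7c are follow-up only.

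- Treated at baseline: one session, or two with a touch-up. The ceiling is 8 mL per session (protocol 6.5.2), so the first course can reach 16 mL.
- Controls first treated at Month 12: one session.
- Re-treatment: one session, at most 8 mL.

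**3. Expected percentages at equal risk per session.** From the documents: about 168 subjects randomised to GP0109 and 56 to control. Assumed, because the documents are silent: risk per session p = 20%, touch-up share t, and 45 of the 56 controls taking treatment at Month 12.

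Independent sessions, baseline-treated subjects: p + t·p(1 − p).

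- t = 50%: 0.20 + 0.50 × 0.16 = 28.0%
- t = 30%: 0.20 + 0.30 × 0.16 = 24.8%

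Correlated sessions: subject risk follows a beta(0.4, 1.6) distribution, with mean 0.20 and within-subject correlation 1/3. The probability of no event in two sessions is (1.6 × 2.6)/(2 × 3) = 0.693, so two-session incidence is 30.7%. At t = 50%: 0.5 × 0.20 + 0.5 × 0.307 = 25.3%.

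Pooling in the controls, as the SAP does: (168 × baseline-treated value + 45 × 0.20)/213. The break-even ratio is the pooled value divided by 20%.

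| Case | Baseline-treated | SAP initial category | Re-treatment | Break-even ratio |
|---|---|---|---|---|
| t = 50%, independent | 28.0% | 26.3% | 20% | 1.32 |
| t = 50%, correlated | 25.3% | 24.2% | 20% | 1.21 |
| t = 30%, independent | 24.8% | 23.8% | 20% | 1.19 |

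**4. Masking of a higher risk.** Re-treatment looks lower only while its true risk is below the break-even. A true 25% prints as lower in the first case (25% against 26.3%) but as higher in the other two (against 24.2% and 23.8%). With independent sessions, all 56 controls pooled in, p from 1% to 50% and t from 25% to 75%, the break-even runs from 1.09 to 1.56.

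**5. Limits.** With t = 0 the ratio is 1.00. If exactly the same subjects react at both sessions, subject incidence does not rise at all. Events per baseline-treated subject still rise by a factor of 1 + t.

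**6. Unequal windows.** This matters for all-cause AEs. Assume a background of 2% per month, no treatment effect and half of the baseline-treated subjects re-treated.

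- 12 months: 1 − e^(−0.24) = 21.34%
- 24 months: 1 − e^(−0.48) = 38.12%
- Baseline-treated: (21.34% + 38.12%)/2 = 29.73%
- With 45 controls followed for about 12 months: (168 × 0.2973 + 45 × 0.2134)/213 = 28.0%, against 21.3% for re-treatment

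The window therefore acts in the same direction as the session count.

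**The case against.** The planned grouping is disclosed, and it fits the regimen: a first course is an injection plus an optional touch-up, and incidence per course is a legitimate summary. No visible objective, hypothesis or test compares re-treatment with first treatment. Table layouts are in a companion document (SAP 2.1.2), so even the side-by-side presentation is an inference. All of this stands, and it is why the course-level table should stay.

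Acute reactions are also collected in a 28-day diary after each session (SAP 1.4). The section that analyses them, SAP 2.5.3, is redacted and may already be by session. That stands too; the point concerns the AE tables in SAP 2.5.2.

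Event counts, onset measured from the most recent session and subject listings are planned, so session rates could be recovered. A reader might infer that the information is lost; it is not. It is simply not tabulated, and event counts alone do not cure the imbalance because they also rise with the number of sessions.

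A reader might further infer that re-treatment will look safer even when its risk per session is higher. The documents do not support that. They give no touch-up share, AE rate or within-subject correlation, and two of the three cases above print a true 25% correctly as higher.

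**Conclusion.** The mismatch in sessions and follow-up is plain in both documents, and its direction at equal risk is clear. The re-treatment percentage can look lower when the touch-up share is above zero and some touch-up subjects react only at the touch-up. Late-treated controls dilute this; the longer initial window adds to it for all-cause events. The illustrative size is 24% to 26% against 20%, on the assumptions p = 20%, t of 30% or 50%, and 45 controls treated. Masking of a truly higher risk is possible only below the break-even and should be stated as conditional.

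No endpoint, test or sample size is affected. This is an inexpensive improvement to descriptive safety reporting, not an error that undermines the trial.

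**What to change.** Keep the course-level table. Add to SAP 2.5.2, with a matching line in protocol 10.5, a table of related AEs and of all AEs by injection session:

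- initial injection at baseline
- touch-up
- re-treatment at Month 12
- first treatment of controls at Month 12

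For each row, use the subjects injected at that session as denominator, and count events with onset in the same fixed window, for example within 28 days and before the next session. That matches the diary period. It also avoids overlap, since a month is 28 days in this study and the touch-up visit falls 28 to 35 days after baseline. At equal risk per session, and leaving selection aside, the expected ratio between rows is then 1.00.

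Base any descriptive statement on first versus repeat treatment on this table. Note beside it that both groups are selected: touch-up subjects because optimal improvement had not been reached, re-treated subjects because improvement was not maintained. Later events remain covered by the course-level table and the late-onset listing.

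The cost is SAP wording and one more table from session and onset dates already collected. The drawback is smaller denominators: at t = 30%, for example, the touch-up row would hold about 168 × 0.30 = 50 subjects.
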